### 6.2 Sample Size Calculation

It is an observational and descriptive study. As far as we know, no data have been published in the literature on the proportion of adverse effects / complications associated with the administration of QETA with 100 micron microspheres, so it has not been possible to make a sample size predetermination based on data previous. It is intended to include 10 patients per center, which would make a total of 130 patients. With this sample size, an accuracy of 1.71% can be achieved in the estimation of a proportion through a bilateral asymptotic confidence interval of 95.00%, assuming that the proportion of the event is 1.00%.

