**SUMMARY**

Object of the investigation	Embozene TANDEM™ 100 µm microspheres
Full Title	Multicenter spanish observational, prospective study to evaluate the safety of transarterial Chemoembolisation (TACE) with tight calibrated and doxorubicin-releasing microspheres of 100 microns in the treatment of Hepatocellular Carcinoma (HCC)
Study Identifier	FJD-TAN-2014-01. Version 1.1, March 15 th , 2015
Study Description	Prospective Post-authorization study of follow-up (EPA-SP)
Promotor	[name], MD, PhD Vascular and Interventional Radiology Service Ramon y Cajal University Hospital. [name]. [contact] [contact]
Principal Investigator	[name], MD, PhD Vascular and Interventional Radiology Service Ramon y Cajal University Hospital. [name]. [contact] [contact]
Primary Objective	Safety and tolerability of DEB-TACE of non-resectable HCC, using 100-µm doxorubicin-loaded microspheres
Secondary Objectives	6-, 12- and 24-month local tumor response and 2-year Over All Survival
Number of Investigators	10 Spanish University Hospitals (See annexed II)
Number of participants	130
Inclusion Criteria	Confirmed diagnosis of HCC, Subject is competent and willing to provide written informed consent, Adults (male or female) patients ≥ 18 years of age, ECOG performance status is 0 – 1 or Child-Pugh classification is A, B7, Multinodular or single nodular tumor ≥3 – 9 cm, No invasion in the major blood vessels, Proper blood, liver, renal, heart function: testing result within 2 weeks of start, No current infections requiring antibiotic therapy, Not actively on anticoagulation drugs, Measureable disease per the modified Response Evaluation Criteria in Solid Tumors (mRECIST), Life expectancy ≥ 6 months
Exclusion Criteria	(ECOG performance status ≥2; or Child-Pugh class B8 or C, Bilirubin levels >3 mg/dl, HCC with large vessel or biliary duct invasion, diffuse HCC or extrahepatic spread, Patients in which any of the following are contraindicated or present (The use of doxorubicin, MRI or CT scans, Hepatic embolization procedures, WBC < 3000 cells/mm  , neutrophil < 1500 cells/mm  , Cardiac ejection fraction < 50 percent, Elevated creatinine greater than or equal to 2.5 mg/dl, Impaired

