## 1 OBJECTIVES OF THE STUDY

### 1.1 Primary Objective

The primary objective is to evaluate the **tolerance and safety** of TACE with TANDEM™ 100 $\mu$  microspheres preloaded with doxorubicin, describing:

- Appearance and intensity of post-embolization syndrome in the 1st week after treatment
- Major adverse events during the 30 days after TACE.
- Minor adverse events during the 30 days after TACE.
- Mortality derived from treatment.

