## 2 STUDY DESIGN

The study has been conceived as a multicenter, international, observational, post-authorization, prospective follow-up study (EPA-SP). It is planned to include between 100 and 150 patients with non-removable HCC treated with the 100  $\mu$ m Embozene TANDEM™ microspheres (drug-releasing microparticles with doxorubicin loading) for enhanced cytotoxic transarterial embolization therapy with hepatocellular carcinoma microparticles.

10 University Hospitals of Spain with recognized experience in treatments with TACE will participate. Each center must recruit a minimum of 5 patients.

All the associated researchers are certified in Vascular and Interventional Radiology with recognized experience in liver cancer intervention, in the administration of small embolic microspheres, in the management of microcatheters and in ultraselective catheterization.

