### **3.4 Expected number of participants and justification**

It is an observational and descriptive study. As far as we know, no data have been published in the literature on the proportion of adverse effects / complications associated with the administration of QETA with 100 micron microspheres, so it has not been possible to make a sample size predetermination based on data previous. It is intended to include 10 patients per center, which would make a total of 130 patients. With this sample size, an accuracy of 1.71% can be achieved in the estimation of a proportion through a bilateral asymptotic confidence interval of 95.00%, assuming that the proportion of the event is 1.00%.

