## 6 STATISTICAL ANALYSIS PLAN

### 6.1 Statistic analysis

A descriptive analysis of the variables included in the study will be carried out. Descriptive statistics will be calculated, including frequencies and percentages for categorical variables and means  $\pm$  standard deviations or medians with interquartile ranges for continuous variables. Univariate analysis is planned to identify variables related to developing complications, using Chi-square tests. To identify risk factors related to mortality, univariate logistic regression models will be constructed. For survival analysis, Kaplan-Meier curves will be plotted, and log-rank tests are going to be used to evaluate differences between the curves. A column graph graft creation is planned to show the tumor response. In all cases where possible, the 95% confidence interval significant at  $p<0.05$  will be calculated. All effects are considered. All statistical analysis will be performed with the SAS 9.4 (SAS Institute Inc., Cary, NC, USA).

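### Ten patients at each of ten hospitals makes 100, not 130, and the only confidence interval named for a proportion is unsuitable for the rare safety events it is applied to

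*Combined protocol and SAP*

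**What the plan says.** **Counts.** Section 3.4 states: "It is intended to include 10 patients per center, which would make a total of 130 patients". Section 6.2 repeats the sentence. The summary lists "10 Spanish University Hospitals (See annexed II") and a total of 130 participants. Section 2 says "10 University Hospitals of Spain with recognized experience in treatments with TACE will participate". It adds two further figures: "Each center must recruit a minimum of 5 patients", and "It is planned to include between 100 and 150 patients with non-removable HCC".

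**Precision.** Sections 3.4 and 6.2 justify the number by saying that "an accuracy of 1.71% can be achieved in the estimation of a proportion through a bilateral asymptotic confidence interval of 95.00" percent, with the event proportion assumed to be 1.00%.

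**Analysis.** Section 6.1 promises intervals in general terms ("In all cases where possible, the 95% confidence interval significant at" p<0.05) and names no method for a proportion. No exact or score interval is mentioned anywhere in the document.

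**What the intervals would describe.** The primary objective (section 1.1 under Objectives) is tolerance and safety. Its items include "Major adverse events during the 30 days after TACE" and treatment-related mortality.

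**The concern.** There are two separate problems: one is arithmetic and the other is a choice of method.

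First, the number of centres, the patients per centre and the total cannot all be right. The stated precision depends on the total, so a reader cannot tell which sample size the 1.71% will belong to.

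Second, the one interval method the plan names for a proportion is the large-sample (Wald) interval, and it is applied at a 1% event rate with about 1.3 expected events (130 × 0.01). The approximation breaks down there. For rare harms the result a reader needs is the upper limit: how high the true rate could still be. If the Wald interval were carried into the report, that limit would err towards reassurance. With no deaths among 130 patients it would read 0%.

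**Working it through.** **Inputs.** 10 hospitals (summary, section 2); 10 patients per centre and N=130 (3.4, 6.2); range 100–150 and minimum of 5 per centre (section 2); two-sided 95% asymptotic interval, half-width 1.71%, event rate 1% (3.4, 6.2).

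**Step 1: counts.**
- 10 centres × 10 patients = 100.
- 130 requires 13 × 10: either 13 centres at 10 patients, or 10 centres at 13 patients.
- The per-centre minimum secures 10 × 5 = 50.

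**Step 2: the plan's own precision figure.** Wald half-width = 1.96 × √[p(1−p)/n].
- n=130, p=0.01: 1.96 × √(0.01 × 0.99/130) = 1.71%. The plan's figure is reproduced.
- n=100: 1.95%. n=150: 1.59%.
- As a planning statement the figure holds. With X ~ Bin(130, 0.01), the estimate lies within 1.71 points of 1% when X ≤ 3, and P(X ≤ 3) = 95.8%.
- The interval 1.00% ± 1.71% nevertheless extends below zero, a sign that the approximation is strained.

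**Step 3: coverage of the interval computed from data.** Binomial probabilities are summed over every X whose Wald interval contains 1%, at n=130.
- X=0: probability 0.99^130 = 27.1%, interval 0% to 0%, misses.
- X=1 to 5: the interval contains 1%.
- X ≥ 6: probability 0.2%, lower limit above 1%, misses.
- Coverage = 100% − 27.1% − 0.2% = 72.7%. Given at least one event, it is 99.7%.
- At the ends of the planned range, coverage at a 1% rate is 63.3% (n=100) and 77.8% (n=150).
- For comparison at n=130 and 1%: Wilson 95.8%, Clopper-Pearson 99.0%.

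**Step 4: other event rates, n=130.** Wald coverage is 92.3% at 2%, 88.9% at 5% and 94.4% at 10%. The probability that the upper limit falls below the true rate (nominally 2.5%) is:

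| True rate | Wald | Clopper-Pearson |
|---|---|---|
| 1% | 27.1% | 0% |
| 2.5% | 16.1% | 0% |
| 5% | 10.6% | 1.0% |

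**Step 5: upper 95% limits at low counts, n=130.**

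| Events | Wald | Clopper-Pearson | Wilson |
|---|---|---|---|
| 0 | 0% | 2.80% | 2.87% |
| 1 | 2.27% | 4.21% | 4.23% |
| 2 | 3.65% | 5.45% | 5.44% |

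**Step 6: commoner outcomes.** The documents give no expected rate for outcomes such as post-embolisation syndrome. If 30–50% is assumed, the Wald half-width at n=130 is 7.9 to 8.6 points, four to five times the stated 1.71.

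**The case against.** The strongest reply is that the asymptotic interval appears only in a planning statement. That statement is correctly calculated and, on its own terms, true. Section 6.1, which governs the analysis, names no method, so nothing obliges anyone to report 0% to 0%. On this view the second problem is an omission, cheaply cured before analysis. This largely stands: 1.71% is not an arithmetic error, and the false reassurance is conditional on the planning method being used for reporting. It does not remove the point. No passage excludes that use, no other method is offered, and the gap concerns the primary objective.

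On the counts, 130 lies within 100–150, a floor of 5 per centre is compatible with it, and unequal recruitment could reach it. The centre annex is not in the text available for review, so the centre count may simply be out of date. All of that is fair, but the sentence derives 130 from 10 per centre, and with 10 hospitals it does not follow. The effect on precision is modest: 1.95% instead of 1.71% if the total is 100.

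Averaged over the possible outcomes at a 1% rate, the half-width is 2.19 points for the exact interval and 2.13 for Wilson. Setting these beside 1.71 mixes an average with a value evaluated at exactly 1%. The upper limits at 0, 1 and 2 events are the cleaner comparison, and they lead to the same conclusion.

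**Conclusion.** Both parts hold, and the plan should be corrected.

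The contradiction in the counts is plain. The total of 130 is stated consistently in the summary, 3.4 and 6.2, and it is the number that reproduces 1.71%. The error is therefore most likely in the centre count or the per-centre figure, but the available text does not settle which.

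The named interval is unsuitable at the plan's own assumed rate. The 72.7% is specific to n=130 and a 1% rate, and is an exact binomial result assuming independent patients with a common rate. The excess of upper limits that are too low persists at 2.5% and 5%. By 10% coverage is close to nominal, so the defect concerns rare events. For common events the interval is acceptable, but 1.71% does not describe their precision.

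**What to change.** 1. Make the number of centres, patients per centre and total agree in the summary and sections 2, 3.4 and 6.2, and restate precision for the resulting total.
2. In 3.4 and 6.2, replace the asymptotic interval with an exact (Clopper-Pearson) or Wilson 95% interval. Name the same method in 6.1 for all safety proportions.
3. State precision over a range of rates. With the exact interval at n=130, for example: no events, upper limit 2.8%; one event, 0.02% to 4.2%; about ±8 to 9 points if a rate of 30–50% is assumed.

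Items 2 and 3 are text changes that need no extra patients and leave collected data untouched. The price is a less favourable stated precision, and some conservatism if the exact interval is chosen (99.0% coverage at a 1% rate, against 95.8% for Wilson). Item 1 is a text correction if 130 is the working total. If it alters the number of centres or the per-centre target, it is a recruitment change and the protocol must say so.

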## 7 ADVERSE EVENTS

### 7.1 Definition

Adverse Event is considered to be any adverse medical event that occurred to a patient or to a subject that participates in a clinical investigation even if it does not necessarily have a causal relationship with it. An Adverse Event may also be any unfavorable or unexpected sign, including an abnormal laboratory finding, symptom, or illness temporarily associated with the investigation, whether or not related to it.

This study is observational, so the patient is not exposed to a higher risk than usual clinical practice. However, as part of the descriptive study, a record of adverse events will be carried out, the rules of which are described below:

### 7.2 Detection and documentation

It is the responsibility of the investigator to document all adverse events that occur during the study. At each visit / evaluation, all adverse events observed by both the researcher, and one of his clinical collaborators, such as those reported by the subject spontaneously or in response to a direct question, will be evaluated by the investigator and noted in the section on Adverse events in the subject's data collection notebook.

Adverse events must be recorded at each evaluation visit throughout the study. The nature of each event, the start time after the procedure under evaluation, the duration, severity and relationship with it should be established. The details of any corrective treatment must be recorded on the corresponding pages of the data collection notebook. The initial symptomatology must be well documented at the selection visit. It is important to correctly collect the baseline information in order to interpret the data of subsequent visits.

Follow-up of adverse events: Investigators should monitor subjects with adverse events until they have decreased, disappeared or until the process has stabilized. Reports regarding the course of the evolution of the subject should be sent to the clinical trial monitor.

### 7.3 Severity assessment

30-day mortality, minor and major adverse events after Tandem-100 DEB-TACE were assessed in accordance with CTCAE 4.03 criteria (33)

The maximum intensity should be assigned one of the following categories:

- **Minor:** An adverse event easily tolerable by the subject, causing minimal discomfort and not interfering with daily activity.
- **Major:** Any adverse event or adverse reaction that, at any dose, causes death, threatens the life of the subject, necessitates hospitalization or prolongation of the subject, causes permanent or significant disability or disability, or results in an anomaly or congenital malformation. For the purposes of its notification, suspicions of adverse events or adverse reactions that are considered medically important will be treated as serious, even if they do not meet the above criteria.

## 8 ETHICAL ASPECTS

### 8.1 Clinical Research Ethics Committee, Institutional Review Board (IRB)

Before the implementation of this study, the protocol, the proposed informed consent form and the patient information sheets must be reviewed by the IRBs of the participating centers. The IRB of the Jiménez Díaz Foundation University Hospital will act as a Reference IRB. A signed and dated document confirming that these documents have been approved by the IRB must be delivered to the promoter, together with the name and position of the president and members of the IRB.

## 8.2 General considerations

This study should be carried out in accordance with the protocol and with the standards of good clinical practice, as described in:

- Harmonized Tripartite Standards of ICH E6, for Good Clinical Practice of 1996.
- Directive 2001/20 / EC.
- Declaration of Helsinki and amendments concerning medical research in humans.
- Order SAS / 3470/2009
- Biomedical Research Law 14/2007

The researcher agrees, with the signing of this protocol, to follow the instructions and procedures described therein and will therefore comply with the principles of Good Clinical Practice on which it is based. Once the protocol is signed, it should not be modified without the written agreement of both the promoter and the principal investigator, and with the consent of the Clinical Trials Ethics Committee.

## 8.3 Patient information

The researcher must explain to each subject the nature of the study, its purposes, procedures, expected duration and the potential risks and benefits related to participation in the study, as well as any inconvenience this may entail. Each participant should be advised that their participation in the study is voluntary and that they can leave the study at any time, without affecting their subsequent medical treatment, or their relationship with the treating doctor.

Informed consent will be provided by standard writing, in language easily understood by the participant. The subject must have sufficient time to read and understand the explanations before dating and signing the informed consent and should receive a copy of the signed document. No subject can be included in the study without previously giving their informed consent.

## 8.4 Confidentiality and access to data

La confidencialidad de los datos personales de los sujetos se mantendrá, aunque sujeta a la necesidad, por parte del monitor, de verificar los datos originales frente a la historia clínica del sujeto. En el cuaderno de recogida de datos y en toda la correspondencia del estudio figurará tan solo el código del paciente y el código del estudio. El promotor no guardará ningún documento con el nombre de ningún sujeto. En todo momento se respetará y cumplirá la Ley Orgánica 15/1999, de 13 de diciembre, de protección de datos de carácter personal.

Toda la información revelada por el promotor al investigador será tratada de manera estrictamente confidencial. El investigador solo hará uso de esta información para el estudio que se describe en este protocolo. Se compromete, además, a no revelar dicha información a terceros, salvo a otros colegas o empleados que participen en la

ejecución del estudio y que se hallen asimismo vinculados por las obligaciones de confidencialidad.

## 8.5 Financial Report

This study is an independent project sponsored by the Spanish Society of Vascular and Interventional Radiology (SERVEI) that does not have specific funding for its realization. This is an observational study that does not include additional procedures to those performed in routine clinical practice. Neither the study researchers nor the patients will receive any remuneration for their participation in it (economic report 0). The exemption of evaluation and administrative management fees is requested from the IRB.

# 9 PRACTICAL ISSUES

## 9.1 Responsibilities of all study team

Researcher: Researchers will follow the rules of Good Clinical Practice and will know and follow the corresponding Standardized Work Procedures. All the information collected during the study will be recorded directly in the data collection booklet, which is attached as annex I. When a correction is made, the date and initials of the person making it should be noted.

Auxiliary staff: Auxiliary staff will follow the instructions given by the researcher regarding the extraction of blood samples, their handling and other complementary examinations.

Monitor: You must attest that the information collected in the protocol is truthful, for which you must have all kinds of facilities by the research team to carry out their work.

Sponsor: He will be responsible for ensuring compliance with the relevant legal regulations and for providing the medication under study.

## 9.2 Protocol deviations

When a situation occurs that causes a deviation from the protocol, the deviation will be only for that subject. Researchers present in such circumstances will fully document the deviation and reason in the CRD. In the event that the deviation has to do with the inclusion / exclusion criteria, the researchers will contact the clinical monitor by telephone to inform them of such deviation.

## 9.3 Amendments to the protocol

Neither the investigator nor the monitor nor the sponsor will modify this protocol without first obtaining the consent of the other parties. The modification must be documented in writing. Any change in the research activity, except those necessary to eliminate an immediate apparent risk to the volunteer, must be reviewed and approved by the IRB before implementation. The promoter must send the amendments to the protocol to the health authorities, and the modifications may require the revision and approval of the IRB

## 9.4 Acceptance of the researcher

The researcher's commitment is included in the documentation submitted to the IRB.

